## **Study Protocol**

The study will be a randomized trial in 50 community-dwelling older adults with early awakening insomnia who live at home, using a within-subject crossover design. The control condition will be a red light mask; the intervention will be a blue light mask (individualized to the patient's light exposure and circadian rhythm). Subjects will use each condition for eight weeks, with the intervention order counterbalanced across subjects, a two-week baseline observation period, and a two-week washout period between the two study conditions. Outcomes will be assessed at baseline and 8 weeks for all measures except for (a) side effects, adverse effects, and protocol deviations, which will be monitored weekly, and (b) clinical eye examinations, which will be conducted at baseline and at the end of each study condition.

Individually Tailored Lighting System to Improve Sleep in Older Adults

NCT01855126

November 5, 2018

Statistical Analysis

We will determine whether the lighting treatments significantly affect the primary outcomes, the nighttime sleep measures (minutes of sleep, sleep onset latency, sleep efficiency, and circadian rhythmicity from actigraphy data; PSQI score; MALSQ score) and safety measures, as well as the secondary endpoints. The primary analytic strategy for the efficacy analyses will employ linear mixed models with measures from the actigraph data (a fourteen-day baseline, plus two seven-day intervention data collection periods for each treatment condition) or one of the survey sleep measures (two observations per treatment condition) as the dependent variable, a random effect for study participant, and a fixed effect for treatment (i.e. a dummy variable for the experimental condition, with the control condition as the reference category). These analyses allow for different numbers of observations for different participants. As part of data cleaning prior to analysis, actigraph data recorded while the monitor is not worn will be identified and removed from the analyses. This will include periods identified as such in the subjects' sleep logs, in addition to actigraphy data in which no activity is present for more than 30 consecutive minutes, and days that contain more than 10% of missing data, and data sets with fewer than 2 days of valid data. The balanced assignment of the two intervention sequences is designed to minimize any adverse impact with respect to period and carryover effects, as is use of a washout period in the experimental design. However, we can explicitly test for a period effect by including a dummy variable in the linear mixed model (with period one as the reference). We will also adjust for covariates that may be found to be associated with night-time sleep, such as gender, age, cognitive status, functional status, baseline sleep disturbance and sedative medication load; however, because of the crossover

nature of the study, in which participants serve as their own controls, it is not expected that covariate adjustment will markedly alter estimates of treatment effect.

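### The SAP makes six sleep measures primary with no lead outcome, success rule or multiplicity adjustment, so any one nominally significant result could be presented as success

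*SAP*

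**What the plan says.** The opening sentence of the SAP's Statistical Analysis section sets the aim: "We will determine whether the lighting treatments significantly affect the primary outcomes". It identifies these as "the primary outcomes, the nighttime sleep measures" and lists them as "minutes of sleep, sleep onset latency, sleep efficiency, and circadian rhythmicity from actigraphy data; PSQI score; MALSQ score". That is four actigraphy measures and two questionnaire scores. The sentence then adds "and safety measures, as well as the secondary endpoints", which leaves unclear whether safety belongs with the primary outcomes or beside them.

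On method, the same section says "The primary analytic strategy for the efficacy analyses will employ linear mixed models with measures from the actigraph data", or with "one of the survey sleep measures (two observations per treatment condition) as the dependent variable". Each model has one treatment term, blue light against red light. For the questionnaires this is expressly one model per score; for actigraphy it is the natural reading of the plural.

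The protocol (Study Protocol) gives the setting: "The study will be a randomized trial in 50 community-dwelling older adults with early awakening insomnia", in a two-condition crossover. It names no primary outcome. Neither document states a significance level, a testing order, a composite, a rule that any one or all six must be significant, or a multiplicity adjustment.

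**The concern.** Followed as written, the plan yields at least six unadjusted primary treatment tests and no rule for combining them. A reader cannot tell beforehand which pattern of results would count as the trial succeeding. If one measure reached nominal significance and five did not, the result could be reported either as a positive primary finding or as a largely negative trial, and the SAP could not settle the matter.

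Leaving the rule open also allows it to be chosen after the results are seen. If it became any one of six, the chance of a false-positive primary claim would exceed the per-test level at every correlation short of perfect.

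**Working it through.** The documents give no error rate, alpha or power, so there is no stated figure to reproduce. What follows is a scenario calculation.

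**Inputs**
- Number of tests: 6, from the SAP's list of primary sleep measures.
- Level per test: two-sided 5%. Assumed.
- All six null hypotheses true, and any one significant measure counts as success. Assumed.
- Correlation between test statistics: not stated, so varied from 0 to 0.95.
- Sample size: 50, from the protocol. It enters only the power cost.

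**Step 1. Independent tests, and the upper bound.** 1 − 0.95^6 = 0.265. Under any dependence the chance cannot exceed 6 × 0.05 = 0.30.

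**Step 2. Correlated tests.** For six standard-normal statistics with common correlation ρ and c = 1.96, the chance of at least one false positive is

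1 − ∫ [Φ((c − √ρ·u)/√(1−ρ)) − Φ((−c − √ρ·u)/√(1−ρ))]^6 φ(u) du.

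Simulation with 1,000,000 draws agrees. The last two columns come from the same simulation.

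| ρ | At least one of six significant | All six significant | Holm's first step (0.05/6) |
|---|---|---|---|
| 0 | 0.265 | 0.000 | 0.049 |
| 0.3 | 0.241 | 0.000 | 0.046 |
| 0.5 | 0.207 | 0.0005 | 0.042 |
| 0.7 | 0.164 | 0.003 | 0.033 |
| 0.8 | 0.139 | 0.007 | 0.028 |
| 0.9 | 0.108 | 0.015 | 0.021 |
| 0.95 | 0.089 | 0.023 | 0.017 |

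**Step 3. A mixed correlation pattern.** Take three actigraphy sleep measures correlated 0.5 to 0.8 with each other, the two questionnaires 0.5 to 0.7, and all other pairs 0.2 to 0.3. The chance is 0.203 to 0.237.

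**Step 4. Only three nulls true.** The chance that at least one of those three is falsely significant is 1 − 0.95^3 = 0.143 if independent, and about 0.10 at correlation 0.8.

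**Step 5. An all-six rule.** The all-six column applies only when every null is true. With five measures strongly affected and one null, a wrong declaration needs just that one test to be falsely significant; simulation gives 0.050 at correlations from 0 to 0.95. The rule therefore holds the error at or below 5%, but not below 2.5% in general.

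**Step 6. The count.** If the wording adds a single seventh test, the independent figure is 1 − 0.95^7 = 0.302, and at correlation 0.95 it is 0.092.

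**Step 7. Power cost of Holm.** Assume 50 completers (25 per sequence), a within-person difference adjusted for period, 48 degrees of freedom, and 80% power at 5%. This corresponds to a standardized difference of 0.404, that is, a noncentrality of 0.404 × √50 = 2.86.
- One measure alone affected: at Holm's first threshold, 0.05/6 = 0.0083, power is 54.7%. Restoring 80% there would need a standardized difference of 0.511.
- All six affected equally, full Holm: per-measure power is 66.3%, 65.6% and 64.3% at correlations 0.3, 0.5 and 0.8 with t-tests, and 67.4%, 66.8% and 65.5% on a normal approximation. That is about 64 to 67%.

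**The case against.** The strongest reply is that the inflated error belongs to a rule the SAP does not contain. Its wording also fits six measure-by-measure reports, each keeping its own per-test error. A reader might infer that the plan declares success on any one measure, or that this trial's false-positive rate is 26%. The documents support neither: they contain no any-one rule, no alpha and no correlations. Full independence is also implausible, since minutes of sleep and sleep efficiency come from the same actigraphy record, and a uniform 0.95 across questionnaires and circadian rhythmicity is no more plausible. The range is a set of scenarios. It is not a bound: perfect correlation would give 5%, and the ceiling under any dependence is 30%.

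This limits the numbers but does not remove the gap. Correlation has been allowed for, and at 0.95 the rate is still nearly double the assumed 5%. If all six were meant to be required, nothing is inflated, but the SAP would have to say so.

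Two further objections stand. The family is not closed at six, because of the safety wording and the undefined circadian parameter. Holm is also expensive in a trial of 50, and a single designated outcome would control the error without that loss for the chosen measure. Nothing in the documents ranks the six measures, so that choice belongs to the sponsor.

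**Conclusion.** The concern holds in this form: at least six primary measures, a separate treatment test for each on the natural reading, and nothing that defines success or controls error across them. Under two-sided 5% tests with all six nulls true and any one counting, the false-positive chance is 26% if independent, about 21% at correlation 0.5, 14% at 0.8 and 9% at 0.95. Alpha, correlations and the any-one rule are assumptions. The absence of a stated rule is not; it can be read directly from the text.

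The plan should be changed, because the gap governs how the main result is read. It does not invalidate any model or estimate.

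**What to change.** Before results are known, add to the SAP:
1. One named parameter for circadian rhythmicity.
2. A statement that the primary efficacy family is the six sleep measures, with safety reported separately.
3. Holm across the six treatment p-values at an overall two-sided 5%. The ordered p-values are compared with 0.05/6, 0.05/5 and so on up to 0.05, stopping at the first failure. Efficacy is claimed only for measures that survive.
4. Unadjusted estimates and confidence intervals reported alongside.

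Holm is suggested because it keeps all six measures primary, as the SAP does, without requiring all six to succeed. If the sponsor prefers, one designated primary outcome with the other five secondary also controls the error, with no power loss for that outcome.

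The cost is a few sentences and no new data. Holm's downside is power. For a measure with an assumed 80% power at 5% and 50 completers (the plan states no power), it falls to about 55% if that measure alone is affected, or about 64 to 67% if all six are equally affected. Holm is also conservative for correlated measures. The documents do not say whether data had been seen by the SAP's date of November 5, 2018; if they had, the rule should be labelled as set afterwards.

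### Baseline actigraphy nights are listed in the outcome but have no level in the treatment dummy, so the blue-versus-red contrast is not secured as written

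*SAP*

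**What the plan says.** The SAP (Statistical Analysis) sets out the primary efficacy model in one sentence. For actigraphy, the dependent variable consists of measures from "a fourteen-day baseline, plus two seven-day intervention data collection periods for each treatment condition". The model has "a random effect for study participant, and a fixed effect for treatment", and the treatment effect is "a dummy variable for the experimental condition, with the control condition as the reference category".

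The Protocol (Study Protocol) fixes what control means: "The control condition will be a red light mask; the intervention will be a blue light mask". It lists baseline apart from both conditions, as "a two-week baseline observation period, and a two-week washout period between the two study conditions".

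Three other SAP statements bear on the point:

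- A period effect may be tested with one further dummy, whose reference level is period one.
- Sleep disturbance at baseline is among the examples of possible adjustment covariates.
- The data-cleaning rules remove non-wear time, days with too much missing data and very short recordings. None of them removes baseline nights as such.

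**The concern.** The outcome covers three kinds of night (baseline, red, blue), but the treatment term has two levels (red, blue). The SAP does not say what happens to the third kind. With a single 0/1 dummy, baseline nights can stay in the model only by sharing the code 0 with red nights. The coefficient then compares blue with a mixture of red and untreated nights.

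That mixture matters because baseline always precedes both masks and is never randomised against blue. Any change common to both mask phases, such as expectation, regression to the mean or habituation, would enter the estimated blue effect. The red mask is there to keep such shared changes out. Counterbalancing and washout do not help, because baseline occupies neither sequence position.

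Two analysts could each claim to follow this text and estimate different quantities for the actigraphy primary outcomes.

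**Working it through.** The documents give no SD, effect size, significance level or power, so there is no stated figure to reproduce. The weights below need only the row counts.

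**Inputs from the SAP.** Baseline has 14 nights. Each condition has 2 × 7 = 14 nights. A completer therefore contributes 14 + 14 + 14 = 42 nights, one third of them untreated. The two sequences are balanced.

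**Method.** With complete, balanced rows, every participant has the same share of blue nights. The random-intercept estimate then equals the within-participant least-squares estimate. Write P for mean red minus mean baseline; the documents give no value for it.

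**Baseline kept and coded 0, no period dummy.** The reference mean is the night-weighted average of red and baseline:

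coefficient = blue − (14 × red + 14 × baseline)/28 = (blue − red) + 0.5P.

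In general the weight on P is b/(b + n), for b baseline nights and n nights per condition.

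**Period dummy added, baseline at its reference.** Set blue = red = P and baseline = 0, and work per night-block, averaging over the two sequences. After centring within participant:

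- The sum of squares is 2/3 for each dummy.
- The cross-product of the two dummies is −1/3 in the blue-first sequence and 2/3 in the red-first sequence, which averages 1/6.
- The cross-product of each dummy with the outcome is P/3.

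By symmetry both coefficients equal (P/3)/(2/3 + 1/6) = 0.4P. In general the weight is b/(1.5b + n), and 14/(21 + 14) = 0.4.

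**Results by row structure**

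| Rows: baseline / red / blue | Weight on P, no period dummy | Weight on P, with period dummy |
|---|---|---|
| 14 / 14 / 14 nights | 0.500 | 0.400 |
| 7 / 14 / 14 nights (half of baseline invalid) | 0.333 | 0.286 |
| 1 / 2 / 2 (one summary per recording) | 0.333 | 0.286 |
| Baseline rows dropped, or given their own level | 0 | 0 |

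If P is positive the bias raises the blue coefficient. If P is negative it lowers it. If P is zero there is none.

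**Precision.** Let s be the nightly SD, with 50 participants and no participant-by-phase variation.

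- Pooled reference: variance = s²(1/14 + 1/28)/50.
- Blue minus red only: variance = s²(1/14 + 1/14)/50.
- Ratio of standard errors = √[(2/14)/(1.5/14)] = √1.333 = 1.155, whatever s is.

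**Illustration under assumptions.** Assume minutes of sleep analysed as nightly rows, s = 60 min, a two-sided 5% test and no true difference between blue and red. The pooled SE is √(3600 × 0.10714/50) = 2.78 min; for blue minus red only it is √(3600 × 0.14286/50) = 3.21 min.

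- P = 5 min gives a bias of 2.5 min, or 0.90 SE, and about 15% rejection.
- P = 10 min gives a bias of 5 min, or 1.80 SE, and about 44% rejection.
- For assumed s of 45 to 75 min, the ranges are 22% to 11% at P = 5 and 67% to 30% at P = 10.

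With baseline dropped, or given its own level, the bias is zero and the test keeps its nominal 5% under these assumptions.

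**The case against.** The strongest reply is that coding baseline as 0 contradicts the SAP itself. The SAP names control as the reference, control is the red mask, and a red-plus-untreated reference is not what it says. The list of recordings can also be read as an inventory of what was collected, with baseline entering only through the covariate for baseline sleep disturbance. A period dummy with two levels fits that reading, and a careful statistician would probably drop the baseline rows.

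Much of this stands. A reader might infer that the SAP prescribes a comparison of blue with red plus untreated nights. The documents do not support that, because no coding for baseline is given. The reply does not close the gap, however. Keeping the rows at 0 conflicts with control as the reference, and dropping them conflicts with listing baseline in the dependent variable. The covariate is only an example, and nothing says that baseline nights then leave the outcome.

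A reader might also take the rejection rates as a forecast for this trial. They are not: P, the nightly SD and the use of nightly rows are all assumed. Only the weights follow from the plan, and 0.5 holds only with complete nights.

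Finally, a reader might extend the point to PSQI and MALSQ, since the Protocol says "Outcomes will be assessed at baseline and 8 weeks for all measures". For these the SAP specifies "one of the survey sleep measures (two observations per treatment condition) as the dependent variable" and lists no separate baseline rows. The same defect is therefore not shown for the surveys.

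**Conclusion.** The point holds for the actigraphy outcomes as a gap in specification. Baseline is placed in the dependent variable, neither the treatment dummy nor the period dummy has a level for it, and no stated rule removes it. The text does not deliver the intended blue-minus-red contrast without a change.

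The size is conditional on baseline nights being kept and coded 0. The bias is then half the red-minus-baseline difference with complete 14/14/14 nights, or 0.4 of it with the period dummy at its reference for baseline. The weight moves with missing days. Its direction depends on whether red nights are higher or lower than baseline, which the documents do not say. This should be fixed before analysis, because it concerns the primary contrast and is simple to settle.

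**What to change.** State in the SAP how baseline actigraphy enters the model. Either of these works:

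1. Restrict the dependent variable to red and blue intervention nights, with each participant's baseline mean as an optional covariate.
2. Keep baseline nights in the outcome, with a three-level condition factor (baseline, red, blue), blue minus red as the primary contrast, and a defined period code for baseline rows. Do not also include a baseline actigraphy covariate in that model.

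Both give baseline zero weight in the blue-minus-red contrast, with or without the period dummy. If the list of recordings was meant only as an inventory, say that baseline nights are not part of the outcome.

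The cost is about one sentence and at most one model term, with no change to conduct or data collection. The standard error is about 15% larger than in the pooled model, given equal night counts and no participant-by-phase variation. In the illustration (nightly SD 60 min) it rises from 2.78 to 3.21 min. If red and baseline really were equal, power for an assumed 10-minute effect would fall from about 95% to 88%. The pooled model's extra precision is sound only under that equality, which the plan does not assert.

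### Baseline actigraphy nights enter the outcome under a single blue-light dummy, so change common to both masks is partly credited to blue light; the two survey occasions per condition are also unnamed

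*SAP*

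**What the plan says.** The SAP (Statistical Analysis) fits a linear mixed model to each sleep measure. For actigraphy the dependent variable covers "a fourteen-day baseline, plus two seven-day intervention data collection periods for each treatment condition". For the questionnaires, PSQI and MALSQ, it is "one of the survey sleep measures (two observations per treatment condition) as the dependent variable". Both kinds of measure are listed as primary outcomes.

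The model has "a random effect for study participant, and a fixed effect for treatment", and the treatment term is "a dummy variable for the experimental condition, with the control condition as the reference category". The only time-related term is optional: "we can explicitly test for a period effect by including a dummy variable in the linear mixed model (with period one as the reference"). Baseline sleep disturbance appears among the possible covariates. There is no visit term, no treatment-by-visit term and no stated code for a pre-treatment row.

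The protocol (Study Protocol) gives the schedule: "Outcomes will be assessed at baseline and 8 weeks for all measures except for" two listed exceptions. One exception is "clinical eye examinations, which will be conducted at baseline and at the end of each study condition". The design includes "a two-week baseline observation period, and a two-week washout period between the two study conditions". The protocol does not say whether the questionnaires are repeated after the washout.

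**The concern.** A two-level dummy has no place for data that belong to neither condition. If baseline nights are outcome rows, they can take the value 0, take the value 1, or be missing. The literal value is 0, because a baseline night is not an experimental-condition night. The reference group then mixes untreated nights with red-light nights. The red mask is there to remove change that would occur under either mask, such as regression to the mean or a response to wearing a mask. Pooling lets part of that change back into the blue-light estimate for the actigraphy primary outcomes.

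The questionnaires raise a related question. Two scores per condition could be one before and one at 8 weeks, or two during treatment. The meaning of the coefficient depends on which, and the documents do not say.

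**Working it through.** The documents give no effect size, SD, significance level or power, so there is no planned figure to reproduce. The results for the coefficients need none of these. The rejection and power figures are illustrations that assume 50 completers, a two-sided 5% level and independent residuals of equal variance within person.

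Notation: ΔB and ΔR are the mean changes from pre-treatment under blue and red, and D = ΔB − ΔR.

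**Actigraphy, baseline coded 0**

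1. Rows per person: 14 baseline nights, 2 × 7 = 14 red, 2 × 7 = 14 blue (SAP).
2. With balanced data and a participant intercept, the coefficient is the blue mean minus the mean of all rows coded 0. Measured from baseline: ΔB − (14·0 + 14·ΔR)/28 = ΔB − ΔR/2 = D + ΔR/2.
3. In general the added term is w·ΔR, with w = baseline rows/(baseline rows + red rows). One baseline summary against two red summaries would give w = 1/3.
4. A baseline covariate is constant across a person's rows, so it does not change this within-person contrast.
5. Period dummy, with baseline rows sharing the period-one code: take three equal blocks per person, centre within person and sum over the two sequences. This gives Stt = Spp = 4/3, Stp = 1/3, Sty = (4ΔB − 2ΔR)/3, Spy = (ΔB + ΔR)/3. The treatment coefficient is (Spp·Sty − Stp·Spy)/(Stt·Spp − Stp²) = [(15ΔB − 9ΔR)/9]/(15/9) = ΔB − 0.6ΔR = D + 0.4ΔR. The bias shrinks but remains.
6. Illustration with D = 0, without the period dummy. The standard error is √[(1/14 + 1/28)/50] = 0.046 nightly residual SD. A shared change of 0.1 SD gives a false effect of 0.05, z = 1.08 and rejection of about 19%. A shared change of 0.2 SD gives 0.10, z = 2.16 and about 58%.

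**Questionnaires, if one score is pre-treatment and both rows carry the condition's code**

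1. With equal pre-condition means, the coefficient is (0 + D)/2 = D/2. The period dummy leaves this unchanged.
2. For D = 0.5 residual SD, using 8-week rows only: z = 0.5·√50/√2 = 2.50, power 70%.
3. Both rows pooled: z = 0.25·√100/√2 = 1.77, power 42% by formula and 41% in simulation. The ratio of test statistics is 0.71.
4. With D = 0, simulated rejection is 5% or less for shared changes of 0.25, 0.5 and 1 SD (0.047, 0.047, 0.028), so the test remains valid.

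**Questionnaires, if both scores are on treatment**

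If the earlier score carries a fraction f of the 8-week effect, the coefficient is (1 + f)/2 of it: 0.75 at f = 0.5, and 1 only at f = 1.

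**The case against.** The strongest reply is that the SAP never says baseline nights are coded 0. An analyst could leave their treatment code missing, which drops them, and the mention of baseline sleep disturbance as a covariate suggests baseline was meant as an adjuster. Either handling would remove the bias. But the sentence on the dependent variable includes the baseline, and nothing takes it out again. The plan needs to say which is meant.

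On the questionnaires the reply carries more weight. The actigraphy wording in the same sentence separates baseline from two intervention periods per condition, and the parallel suggests two on-treatment scores. The protocol's schedule is a weak counter-argument, since its summary mentions no second on-treatment actigraphy window either. Against that, the protocol treats eye examinations at baseline and at the end of each condition as an exception, which gives slight support to a different pattern for the other measures, such as a baseline repeated per condition. Neither reading is established, so halving is a conditional result.

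A reader might go further and infer that type I error is inflated for PSQI and MALSQ too. If only on-blue rows were coded 1, the coefficient would be ΔB − ΔR/3, and with D = 0 and shared changes of 0.25, 0.5 and 1 residual SD, simulated rejection is about 17%, 51% and 97%. The documents do not support this. It needs a pre-treatment score in each condition and also a pre-blue row placed in the reference group, whereas the SAP counts survey rows by condition and makes the control condition the reference.

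**Conclusion.** The point holds in two parts of unequal strength.

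For actigraphy, the model read literally estimates D plus half of the baseline-to-red change (0.4 of it with the period dummy and baseline sharing the period-one code). This assumes baseline rows are coded 0 and valid nights are equally numerous. There is no bias if nothing changes under red or if baseline rows are dropped. The 19% and 58% false-positive rates also assume independent nights; they show that a small shared change is enough, and they are not forecasts.

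For PSQI and MALSQ, the omission is certain but the harm is conditional. With one pre-treatment score per condition coded by condition, the estimate is D/2 and power is lost, with no excess of false positives. With two on-treatment scores, the estimate is an average effect, equal to the 8-week effect only if the effect is constant. It would be wrong to conclude that the survey analysis misses the 8-week effect altogether, that it is certain to be diluted, or that two on-treatment scores rule out dilution. Neither document defines the target as the week-8 contrast.

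This should be corrected because it decides what the primary coefficients mean.

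**What to change.** - Do not enter any pre-treatment row as an outcome under the single treatment dummy. Either leave baseline rows out of the outcome and use the study baseline as a covariate, or give them their own level through visit and treatment-by-visit terms. In both cases take the blue-minus-red contrast from on-treatment data. The two actigraphy windows per condition can both stay.
- Name the two PSQI and MALSQ occasions in each condition, state the code of each row, and reconcile the protocol schedule with the SAP.
- If one survey score is pre-treatment, analyse the 8-week scores or take the treatment contrast at 8 weeks. If a score taken just before the second condition is to be a covariate, state the no-carryover assumption or keep that model as a sensitivity analysis.
- If both survey scores are on treatment, keep the averaged contrast and say that it is the target.

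The cost is wording in both documents and one or two model terms. No new data are needed. If both survey scores are on treatment, the survey model stands as written and loses no precision.

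### The actigraphy mixed model has a participant effect but no participant-by-period effect, so its treatment standard error is too small if participants vary between periods

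*SAP*

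**What the plan says.** The Protocol (Study Protocol) describes 50 participants studied "using a within-subject crossover design": "Subjects will use each condition for eight weeks, with the intervention order counterbalanced across subjects". Each person therefore contributes one blue and one red treatment period.

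The SAP (Statistical Analysis) takes actigraphy from a fourteen-day baseline, "plus two seven-day intervention data collection periods for each treatment condition". The primary analysis is a linear mixed model with "a random effect for study participant, and a fixed effect for treatment". It accepts unequal record counts across participants. The only mention of period in the model is optional: "we can explicitly test for a period effect by including a dummy variable in the linear mixed model". The SAP names no participant-by-period term, residual covariance, robust variance or degrees-of-freedom method. It does not say whether an actigraphy record is a night or a window summary.

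For PSQI and MALSQ the SAP has "two observations per treatment condition". The Protocol says "Outcomes will be assessed at baseline and 8 weeks for all measures except for" safety monitoring and eye examinations.

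**The concern.** A participant intercept makes all of one person's records equally correlated, whichever condition they come from. Records within one eight-week block also share whatever is particular to that person in that block, such as illness, season, household changes or an individual response to the mask. The blue-red contrast is a contrast between blocks, so this block-level variation enters its true variance in full. The stated model instead puts it in the residual and averages it over all records, as if each one were separate evidence on treatment.

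The fixed period dummy does not cure this, because it removes one shift common to everybody and leaves the person-specific deviations. Washout and counterbalancing deal with average carryover and period effects. Participants serving as their own controls removes stable differences between people, but not differences between one person's two blocks.

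The four actigraphy measures among the six named primary sleep measures (sleep minutes, onset latency, efficiency, rhythmicity) would have standard errors and p-values that are too small.

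**Working it through.** **Inputs from the documents.** n = 50 participants and two treatment periods each (Protocol, Study Protocol). Two seven-day windows per condition (SAP, Statistical Analysis), hence m = 2 records per condition if each window is summarised, or up to m = 14 if nights are rows. The plan gives no alpha, variance or standard error, so there is no figure of its own to reproduce.

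**Assumptions.** Two-sided 5% level. ρ is the share of within-participant variance that lies between periods; nightly values of 0.05, 0.10 and 0.20 are used for illustration.

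**Formulas (balanced data).** Let σ² be the within-participant variance and g the number of participant-periods with rows (2, or 3 if baseline rows are included).

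- True variance of the blue-red difference: 2σ²[1 + (m−1)ρ]/(mn).
- Variance reported by the participant-only model: 2σ²[1 − (m−1)ρ/(gm−1)]/(mn).
- Ratio, true to reported: [1 + (m−1)ρ] / [1 − (m−1)ρ/(gm−1)]. This exceeds 1 whenever ρ > 0 and m > 1.
- Type I error: 2[1 − Φ(1.96/√ratio)].
- Averaging seven nights removes night-to-night noise, so weekly ρ = ρ/(ρ + (1−ρ)/7), giving 0.27, 0.44 and 0.64.
- Nights correlated only within their own window: ratio = (1+6ρ)/(1−6ρ/27), or with 41 in place of 27 when baseline nights are added.

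**Examples at nightly ρ = 0.10, no baseline rows.**

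- Window summaries: weekly ρ = 0.10/(0.10 + 0.90/7) = 0.4375. Ratio = 1.4375/(1 − 0.4375/3) = 1.68. Type I error 13%.
- Nights, equal correlation across both windows: ratio = (1 + 1.3)/(1 − 1.3/27) = 2.42. Type I error 21%.
- Nights, correlation only within a window: ratio = 1.6/(1 − 0.6/27) = 1.64. Type I error 12.5%.

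**Results at nightly ρ = 0.05, 0.10, 0.20.**

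| Analysed row | Variance ratio | Type I error | With baseline rows |
|---|---|---|---|
| One summary per window | 1.39, 1.68, 2.08 | 10%, 13%, 17% | 9%, 12%, 15% |
| Nights, correlation within window only | 1.31, 1.64, 2.30 | 9%, 12.5%, 20% | 9%, 12%, 19% |
| Nights, equal correlation across windows | 1.69, 2.42, 3.98 | 13%, 21%, 33% | 13%, 20%, 32% |

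At ρ = 0 every entry is 5%. One summary per window with variation specific to the window also gives 5%.

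**Simulation under the null** (n = 50, balanced, 20,000 runs, participant-only model, no baseline rows; nightly ρ 0, 0.05, 0.10, 0.20).

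- Window summaries: 5.0%, 9.4%, 12.8%, 17.7%.
- Nights, equal correlation: 5.1%, 13.5%, 20.6%, 31.6%. At ρ = 0.10 the empirical SD of the estimate was 0.081 against a mean reported standard error of 0.052.
- Nights, within-window correlation, at 0.05, 0.10, 0.20: 8.6%, 12.7%, 19.8%.

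**Remedies with unbalanced data** (REML, 1,500 runs, Monte Carlo standard error about 0.6 points near 5%; remedies tested on 49 df).

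| Setting | Participant only | With participant-by-period term | Mean difference |
|---|---|---|---|
| 4 to 14 nights per condition, ρ = 0 | 4.8% | 4.2% | 6.1% |
| 4 to 14 nights per condition, ρ = 0.10 | 15.9% | 4.8% | 4.9% |
| 1 or 2 summaries per condition, weekly ρ = 0.44 | 9.0% | 4.4% | 4.3% |

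**PSQI and MALSQ.** If both scores in a condition carry the same treatment code, m = 2 and survey ρ of 0.05, 0.10, 0.20 and 0.30 gives 5.8%, 6.6%, 8.4% and 10.3%. If the two scores are a pre-treatment and a week-8 score and only the on-blue score is coded 1, true and reported variance are both (4e/3 + 8c/9)/n, with e the residual and c the participant-by-period variance. There is then no inflation (simulated 5.0% to 5.2% for ρ from 0 to 0.5).

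**The case against.** The mechanism is hard to dispute; the objections concern certainty and size.

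- **One value per condition.** The Protocol lists a single on-treatment time point, week 8, and the SAP does not say that each window is a row. If both windows feed one value per condition, m = 1 and there is no bias. That is true, but the reading fits poorly with an SAP that describes two on-treatment windows apart from baseline and allows for differing record counts.
- **Summaries are the likelier row.** The SAP discards data sets with under two valid days, a rule that makes most sense if each data set is summarised. This is suggestive, and it is a reason not to rest the case on the 20% to 33% figures.
- **The window-summary figures assume that both windows share all the excess correlation.** If half is shared, they fall to 7.2%, 8.7% and 10.7%; if a quarter, to 6.1%, 6.8% and 7.6%. This stands, and it widens the plausible range downwards.
- **An omitted common period shift inflates the residual and offsets part of the error.** At weekly ρ 0.44 and a shift of 0.8 within-participant SD, two simulations gave 8.5% and 9.6% in place of about 13%. The offset is partial and accidental, and it disappears once the period dummy is fitted.
- **The SAP is an outline, and silence is not exclusion.** It does, however, name the random effect it intends, and an analyst following it would fit that model.

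**Conclusion.** The concern holds. Fitted as stated, with at least two on-treatment records per condition, the model understates the treatment variance for actigraphy whenever participant-by-period variation exists. For balanced data with period effects accounted for, the direction is certain. The size is not, because the documents give neither ρ nor the analysed record. With window summaries, type I error runs from about 6% to 17% over nightly ρ of 0.05 to 0.20, depending on how much correlation the two windows share; with nights as rows, it runs from about 9% to 33%. There is no inflation if ρ is zero, if each condition is reduced to one value, or if windows are summarised and the variation is specific to the window. For PSQI and MALSQ the point is conditional on how the two scores are timed and coded. This should be corrected before analysis; confidence in its practical size is moderate.

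**What to change.** Add to the primary actigraphy model a participant-by-period random effect nested in participant, with a small-sample degrees-of-freedom method such as Kenward-Roger or Satterthwaite. Alternatively, analyse one blue-minus-red difference of on-treatment means per participant. The two are equivalent only with balanced data, and the difference analysis drops anyone with only one usable condition, whom the mixed model keeps.

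So that the term can be applied, state whether the actigraphy record is a night or a window summary, and how the two survey observations per condition are timed and coded. If one value per condition is intended, a sentence saying so settles the matter for actigraphy.

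The change needs no new data and about one line of specification. Where between-period variation exists, intervals widen by the square root of the variance ratio: at nightly ρ 0.10, √1.68 ≈ 1.30 for window summaries and √2.42 ≈ 1.55 for nights with equal correlation. Where there is none, they widen by about 2%: the t quantile is 2.010 on 49 df, against 1.976 with four summaries per participant (200 − 50 − 1 = 149 df) or 1.962 with 28 nights (1,400 − 50 − 1 = 1,349 df).
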